7.2 Background Characteristics

Participant Disposition

The number of participants in the following categories will be summarized by treatment group (see Section 7.1) based on the ITT set:

- Safety Set
- Solicited Safety Sets
- **PP Sets**

The number and percentage of participants in each of the following disposition categories will be summarized by treatment group and serostatus, based on the ITT Set:

- Received each study vaccine
- Completed study (A participant who completed 12 months of follow up after the last vaccination received and completed the Month 13 procedures is considered to have completed the study.)

Protocol mRNA-1893-P101

- Prematurely discontinued the study and the reason for discontinuation
- Prematurely discontinued vaccination and the reason for discontinuation

The number of participants that screen fail will be summarized along with the reason for screen failure.

Participant disposition, screen failure, randomization, and analysis set listings will be provided.

7.2.2 Demographics

Demographic information will be listed (including flavivirus serostatus at Screening) and summarized. Descriptive statistics will be calculated for the following continuous demographic and baseline characteristics: age, weight (kg), height (cm), and body mass index (BMI) (kg/m²). Frequency counts will be tabulated for the categorical variables sex, race, and ethnicity. The summaries will be presented by flavivirus serostatus at Screening and by treatment group as defined in Section 7.1 for participants in the Safety set.

For screen failure participants, age (years), weight (kg), height (cm), BMI (kg/m²), as well as sex, race, ethnicity will be presented in a listing.

In addition, an inclusion and exclusion criteria violation data listing will be provided.

7.2.3 Medical History

Medical history data will be coded by system organ class (SOC) and preferred term (PT) using the Medical Dictionary for Regulatory Activities (MedDRA). Medical history data will be presented in a listing.

7.3 Prior and Concomitant Medications

Prior and concomitant medications will be coded using the World Health Organization drug dictionary.

Use of analgesics and/or antipyretics will be recorded by participants on a diary card as absent or present, and participants will indicate if use was for treatment or prophylaxis.

The number and percentage of subjects for each common dictionary medical coded term during the 7-day follow-up period (ie, on the day of vaccination and the 6 subsequent days) and during the 28 day follow up period (ie, on the day of vaccination and the 27 subsequent days) will be summarized by treatment groups as defined in Section 7.1 after each vaccination for subjects in the Safety set. In addition, the number and percentage of

Date Issued: 25May2021

subjects using any analgesic or antipyretic or any prophylactic analgesic or antipyretic will be summarized.

Prior and concomitant medications will be presented in a listing.

7.4 Major Protocol Deviations

A deviation from the protocol is an unintended or unanticipated departure from the procedures or processes approved by the Sponsor and the Internal Review Board (IRB) and agreed to by the investigator. Deviations usually have an impact on individual participants or a small group of participants and do not involve inclusion/exclusion or primary endpoint criteria. Protocol deviations will be assessed to determine if the deviation is a major or minor deviation and this assessment will be recorded in the protocol deviation review plan.

Major protocol deviations will be presented in a listing.

7.5 Study Vaccine Administration

Study vaccine administration data will be presented in a listing.

7.6 Safety Analysis

Safety assessments will include monitoring and recording of solicited AEs (local and systemic reactogenicity events) and unsolicited AEs, SAEs, AESIs, AEs leading to study withdrawal, MAAEs; clinical laboratory test results (hematology, serum chemistry, and coagulation); vital sign measurements; and physical examination findings. The Toxicity Grading Scale for Healthy Adult and Adolescent Volunteers Enrolled in Preventative Vaccine Clinical Trials [DHHS 2007] will be used to categorize unsolicited AEs, abnormal clinical laboratory test results, and vital sign measurements.

All safety analyses will be based on the Safety set, except that the analyses of solicited AEs will be based on the Solicited Safety sets.

7.6.1 Solicited Adverse Reactions

The term "reactogenicity" refers to selected signs and symptoms (ARs) occurring after vaccine administration that the participants are systematically asked to record. Participants will record such occurrences in a diary card on the day of each vaccine administration and for the 6 days after vaccine administration.

Date Issued: 25May2021

The local solicited ARs include injection site pain, injection site erythema, and injection site induration/swelling.

The systemic solicited ARs include fever, generalized myalgia (muscle ache or pain), generalized arthralgia (joint ache or pain), headache, fatigue/malaise (unusual tiredness), nausea/vomiting, chills, and rash.

For erythema, swelling, and fever, grade will be derived based on the measurement recorded on the diary card as noted in Table 2. Other events will be assessed for grade by the investigator based on the Toxicity Grading Scale for Healthy Adult and Adolescent Volunteers Enrolled in Preventative Vaccine Clinical Trials [DHHS 2007] and recorded in the eCRF.

Table 2: Toxicity Grads for Erythema, Swelling, and Fever

| | Grade 1 | Grade 2 | Grade 3 | Grade 4 |
|----------|---------------|---------------|---------------|----------|
| Erythema | 21 - 50 mm | 51 – 100 mm | > 100 mm | |
| Swelling | 21 – 50 mm | 51 – 100 mm | > 100 mm | |
| Fever | 38.0 – 38.4°C | 38.5 – 38.9°C | 39.0 – 40.0°C | > 40.0°C |

Any solicited AR that meets any of the following criteria will be entered as an AE in the eCRF:

- Solicited local or systemic AR leading to the participant withdrawing from the study or the participant being withdrawn from the study by the investigator
- Solicited local or systemic AR lasting beyond 7 days post vaccination
- Solicited local or systemic AR that leads to participant withdrawal from vaccine
- Solicited local or systemic AR that otherwise meets the definition of an SAE
- Laboratory test result or vital sign measurements with a toxicity score of Grade 3 or greater or that is deemed clinically significant by the investigator for any grade

The percentage of participants who report each individual solicited local AR and solicited systemic AR from the time of study vaccination through the following 6 days (Day 1 through Day 7 and Day 29 though Day 35) will be tabulated by grade (including grades 1, 2, 3, and any grade >0), treatment group as defined in Section 7.1, and vaccination (first or second). These summaries will also be presented separately for flavivirus seropositive and seronegative participants.

Date Issued: 25May2021

Duration (in days) of each solicited AR will be summarized by treatment group and vaccination.

All solicited ARs, local solicited ARs, systemic solicited ARs, solicited ARs that are still on-going 6 days after vaccination, and solicited rash events will be presented in separate data listings.

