6.3 Appendix 3: Toxicity Grading Scale Tables

The toxicity grading scales for clinical and laboratory abnormalities are presented in Table 6 and Table 7, respectively. Note that for laboratory abnormalities, grading only occurs if the values are outside of the normal values established by the clinical laboratory. For study-specific laboratory normal ranges and associated toxicity grades, refer to the laboratory manual.

Table 6: Tables for Clinical Abnormalities

Local Reaction to Injectable Product	Mild (Grade 1)	Moderate (Grade 2)	Severe (Grade 3)	Potentially Life-threatening (Grade 4)
Pain	Does not interfere with activity	Repeated use of non-narcotic pain reliever > 24 hours or interferes with activity	Any use of narcotic pain reliever or prevents daily activity	ER visit or hospitalization
Tenderness	Mild discomfort to touch	Discomfort with movement	Significant discomfort at rest	ER visit or hospitalization
Erythema/Redness *	2.5 – 5 cm	5.1 – 10 cm	> 10 cm	Necrosis or exfoliative dermatitis
Induration/Swelling **	2.5 – 5 cm and does not interfere with activity	5.1 – 10 cm or interferes with activity	> 10 cm or prevents daily activity	Necrosis

Abbreviation: ER = emergency room.

Source: Guidance for industry – Toxicity grading scale for heathy adult and adolescent volunteers enrolled in preventative vaccine clinical trials; Tables for clinical abnormalities (DHHS 2007).

^{*} In addition to grading the measured local reaction at the greatest single diameter, the measurement should be recorded as a continuous variable.

^{**} Induration/swelling should be evaluated and graded using the functional scale as well as the actual measurement.

Vital Signs *	Mild (Grade 1)	Moderate (Grade 2)	Severe (Grade 3)	Potentially Life-threatening (Grade 4)
Tachycardia (beats per minute)	101 – 115	116 – 130	> 130	ER visit or hospitalization for arrhythmia
Bradycardia (beats per minute)**	50 – 54	45 – 49	< 45	ER visit or hospitalization for arrhythmia
Hypertension (systolic) (mm Hg)	141 – 150	151 – 155	> 155	ER visit or hospitalization for malignant hypertension
Hypertension (diastolic) (mm Hg)	91 – 95	96 – 100	> 100	ER visit or hospitalization for malignant hypertension
Hypotension (systolic) (mm Hg)	85 – 89	80 – 84	< 80	ER visit or hospitalization for hypotensive shock
Respiratory rate (breaths per minute)	17 – 20	21 – 25	> 25	Intubation

Abbreviation: ER = emergency room.

Note that fever is classified under systemic reactions for grading purposes.

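### SAP Table 2 and protocol Table 6 grade erythema and swelling differently for the first primary endpoint, and SAP Section 8 neither lists nor justifies the difference

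*SAP*

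**What the plan says.** **SAP, Section 7.6.1.** The rule is: "For erythema, swelling, and fever, grade will be derived based on the measurement recorded on the diary card". The Table 2 rows, Grades 1 to 3, are "Erythema | 21 - 50 mm | 51 – 100 mm | > 100 mm" and "Swelling | 21 – 50 mm | 51 – 100 mm | > 100 mm". The Grade 4 cell is empty for both signs but filled for fever. For the remaining solicited reactions: "Other events will be assessed for grade by the investigator". The tabulation paragraph names Grades 1, 2, 3 and any grade above zero.

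**Protocol, Appendix 3, Table 6.** Erythema Grade 1 is 2.5 to 5 cm. Swelling is graded on size and function together: Grade 1 is "2.5 – 5 cm and does not interfere with activity", Grade 2 is "5.1 – 10 cm or interferes with activity" and Grade 3 is "> 10 cm or prevents daily activity". A footnote requires the functional scale for swelling in addition to the measurement. Grade 4 erythema is "Necrosis or exfoliative dermatitis"; Grade 4 swelling is necrosis. Protocol Section 3.5.6 has the investigator confirm and grade reactogenicity by reference to this table.

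**Status of the difference.** SAP Section 2 says the SAP prevails where its methods differ from the protocol's. SAP Section 8 lists two changes: the definition of the All Enrolled Participants Set, and the decision not to compute differences in AE proportions. Neither it nor the SAP document history mentions grading of local reactions.

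**The concern.** The frequency and grade of each solicited reaction is the first primary endpoint in both documents (protocol Section 3.6.1, SAP Section 4.1). The rule that turns a diary entry into a grade is therefore part of the endpoint definition. A reader with the protocol in hand would assume that a Grade 2 or Grade 3 swelling in the results means what Table 6 says it means, and under the SAP it need not.

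The two departures act in opposite directions. The lower size floor adds mild reactions. Dropping the functional criterion lowers the grade of swelling that limits activity, or leaves it ungraded. The any-grade and Grade 1 rows can rise while the Grade 2 and Grade 3 rows fall, so the effects need not cancel.

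**Working it through.** **The plan's own figure.** Protocol Section 3.6.4 and SAP Section 5.2 give the probability of seeing at least one AE among 24 vaccinees per dose. The formula is 1 − (1 − p)^24.
- p = 0.10: 1 − 0.90^24 = 0.9202 (stated 92%).
- p = 0.05: 1 − 0.95^24 = 0.7080 (stated 70.8%).

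Both reproduce. The grading point does not depend on them; they only confirm 24 as the planned group size.

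**Swelling grades side by side.** Inputs are the swelling rows of Table 6 (centimetres converted to millimetres) and SAP Table 2. Diameters are taken as whole millimetres, and Table 6's size-or-function wording is read literally.

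| Diameter | Table 6, no limitation | Table 6, interferes with activity | Table 6, prevents daily activity | SAP Table 2 |
|---|---|---|---|---|
| 20 mm or less | none | 2 | 3 | none |
| 21–24 mm | none | 2 | 3 | 1 |
| 25–50 mm | 1 | 2 | 3 | 1 |
| 51–100 mm | 2 | 2 | 3 | 2 |
| over 100 mm | 3 | 3 | 3 | 3 |

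**Size alone.** The scales differ only at 21, 22, 23 and 24 mm: no grade under Table 6, Grade 1 under the SAP. The same holds for erythema. The boundaries above 50 mm and above 100 mm agree.

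**Function, swelling only (Table 6 grade minus SAP grade, counting ungraded as 0).**
- Prevents daily activity: 3 − 0 = 3 at 20 mm or less; 3 − 1 = 2 at 21–50 mm; 3 − 2 = 1 at 51–100 mm; 3 − 3 = 0 above 100 mm.
- Interferes with activity: 2 − 0 = 2 at 20 mm or less; 2 − 1 = 1 at 21–50 mm; 2 − 2 = 0 at 51–100 mm; 3 − 3 = 0 above 100 mm.

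**Fever.** Both documents use 38.0–38.4, 38.5–38.9, 39.0–40 and above 40 °C. There is no difference.

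**Grade 4.** A rule based only on a diameter cannot return necrosis, so SAP Table 2 yields at most Grade 3 for erythema and swelling.

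**Effect of one regraded participant on a row,** if everyone planned is in the Solicited Safety Set:
- One dose group: 1/24 = 4.2 percentage points. Pooled placebo is the same, since 4 × 6 = 24.
- Seronegative vaccinees in one dose group: 1/20 = 5.0 points.
- Seropositive vaccinees in one dose group: 1/4 = 25.0 points.

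SAP Section 7.6.1 tabulates the two serostatus groups separately, so the last two steps apply to planned tables. Any single reclassification would give the same steps. They say nothing about how many participants would be regraded, and the documents give no such number.

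**The case against.** The other side has a fair case. The protocol leaves analysis detail to the SAP, the SAP prints its cut-offs in full, and it claims precedence. The rule applies alike to every group, and these summaries are descriptive. The 21 mm floor spans only 4 mm and errs towards counting more reactions. Whether function was recorded for swelling depends on a diary card and eCRF that are not part of the documents. Some of the lost information may appear elsewhere: pain is graded by the investigator and its Grade 3 also covers loss of daily activity, and individual listings are planned.

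This narrows the consequence but does not remove the point. Precedence decides which rule is run. It does not tell the reader that the primary-endpoint grade departs from the protocol, or why. Neither the pain row nor a listing corrects the swelling row.

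Four stronger readings are tempting, and the documents do not support them.

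- *Pause decisions would be wrong.* Pause rule 4 counts Grade 3 solicited local events, so a reader might infer that SAP grades could hide a pause. But SAP Section 5.4 sends the statistician to the protocol's own Table 3 criteria, and protocol Sections 3.5.6 and 3.5.7.4 grade reactogenicity on the protocol scale. Nothing says SAP Table 2 feeds the rule.
- *Grade 4 events would disappear.* The SAP's list of tabulated grades is introduced as *including* those grades, so it is not exhaustive. Necrosis is not a listed solicited reaction and may be captured as an unsolicited event, for which SAP Section 7.6.2.1 summarises Grades 3 and 4. Pause rule 2 covers Grade 4 events separately.
- *The scale was switched late.* The SAP document history records no grading change after Version 1.0 of 24 October 2019.
- *The SAP's reliance on protocol Version 2.0 can be ruled out as the cause.* All that can be said is that the protocol's Summary of Changes names no Appendix 3 edit; the Version 2.0 appendix itself is not available.

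**Conclusion.** The point holds as an unreconciled and unlisted difference in how a primary endpoint is graded, and it should be fixed. Two effects are established from the tables alone. Reactions of 21 to 24 mm are Grade 1 only under the SAP. Swelling that prevents daily activity is graded one to three grades lower up to 100 mm, and swelling that interferes with activity one or two grades lower up to 50 mm. The empty Grade 4 cells are a minor addition.

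This rests on taking Table 6's size-or-function wording literally, and on the SAP being programmed as written. The number of participants affected, and so the shift in any reported percentage, cannot be estimated. No effect on the pause rules is shown.

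**What to change.** Reconcile SAP Table 2 with protocol Table 6 so that the primary tabulation uses one stated scale:

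- Recompute the Grade 1 floor from the recorded diameters.
- Use the investigator's functional grade for swelling where it was captured. If it was not, state that as a limitation.
- Add a Grade 4 row for erythema and swelling.
- If the 21 mm, size-only scale was intended, list it in SAP Section 8 with a reason and also tabulate the Table 6 grades.
- Add one sentence confirming which grade is used when the protocol Table 3 pause criteria are evaluated. No change to the rule is proposed.

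The cost is low for the floor, the Grade 4 row and the Section 8 entry: text, table-shell and programming edits on diameters the diary already records. The functional part depends on what the eCRF holds. SAP Section 7.6.1 mentions an investigator grade in the eCRF only for the other reactions, although protocol Sections 3.5.2 and 3.5.6 have the investigator score reactogenicity generally. If the data do not exist, the cost is one sentence of limitation.

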3.4.2.2 Pause Rules

Study pause rules will be continuously monitored during all phases of the study by the investigators, study medical monitor, Sponsor medical lead, IST, and SMC (as warranted). If the investigator, study medical monitor, Sponsor medical lead, IST, or SMC request that the study be paused due to a safety concern, further study vaccine administration in the affected cohort and at higher dose levels will be suspended, but all other planned procedures relating to safety, reactogenicity, and immunogenicity assessments will continue as described in the protocol.

The occurrence of any of the events listed in Table 2, regardless of dosing group, will result in immediate suspension of dosing and enrollment in the cohort. An unscheduled meeting of the SMC will be convened to assess specific data concerns and to make recommendations.

The Sponsor will notify the Center for Biologics Evaluation and Research within 48 hours in the event of a study pause.

Table 2: Pause Rules Based on the Occurrence of a Single Adverse Event and Adjudicated by the SMC

Pause Rule	Adverse Event	Number of Participants per Dose Cohort
1	Any serious adverse event that cannot be reasonably attributed to a cause other than vaccination	≥ 1
2	Any Grade 4 adverse event that cannot be reasonably attributed to a cause other than vaccination	≥ 1
3	Any systemic immediate hypersensitivity reaction within 60 minutes after the study vaccination	≥ 1

Abbreviation: SMC = Safety Monitoring Committee.

Table 3 summarizes safety events that will pause study dosing based on defined threshold levels, which are aggregate incidences relative to the number of exposed participants within a dosing group. An unblinded statistician may be consulted to determine if a pause rule has been met.

Table 3: Pause Rules Based on the Occurrence of Adverse Events in a Proportion of Participants

Pause Rule	Adverse Event	Number of Participants per Dose Cohort ^a	
4	Any Grade 3 solicited local adverse event lasting more than 24 hours in an mRNA-1893 cohort ^b within the 7-day (Days 1-8) post-vaccination period	≥ 20% and ≥ 2 participants/group	
5	Any Grade 3 solicited general adverse event lasting more than 24 hours in an mRNA-1893 cohort ^b that cannot be reasonably attributed to a cause other than vaccination, within the 7-day (Days 1-8) post-vaccination period	\geq 20% and \geq 2 participants/group	

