3.6 Statistical Analysis Plans

3.6.1 Primary Endpoints

The following are the primary endpoints of the study:

• Frequency and grade of each solicited local and systemic reactogenicity AE during a 7-day follow-up period after each vaccination

- Frequency and grade of any unsolicited AEs during the 28-day follow-up period after each vaccination
- Frequency of any MAAE, SAE, and AESI from Day 1 to the EOS Visit at Month 13

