Source: Guidance for industry – Toxicity grading scale for heathy adult and adolescent volunteers enrolled in preventative vaccine clinical trials; Tables for clinical abnormalities (DHHS 2007).

^{*} Participant should be at rest for all vital sign measurements.

^{**} When resting heart rate is between 60 – 100 beats per minute. Use clinical judgment when characterizing bradycardia among some healthy participant populations, for example, conditioned athletes.

Systemic (General)	Mild (Grade 1)	Moderate (Grade 2)	Severe (Grade 3)	Potentially Life-threatening (Grade 4)
Fever (°C) * (°F) *	38.0 – 38.4 100.4 – 101.1	38.5 – 38.9 101.2 – 102.0	39.0 – 40 102.1 – 104	> 40 > 104
Nausea/vomiting	No interference with activity or 1 to 2 episodes/ 24 hours	Some interference with activity or > 2 episodes/ 24 hours	Prevents daily activity, requires outpatient IV hydration	ER visit or hospitalization for hypotensive shock
Diarrhea	2 – 3 loose stools or < 400 g/ 24 hours	4 – 5 stools or 400 – 800 g/ 24 hours	6 or more watery stools or > 800 g/ 24 hours or requires outpatient IV hydration	ER visit or hospitalization
Headache	No interference with activity	Repeated use of non- narcotic pain reliever > 24 hours or some interference with activity	Significant; any use of narcotic pain reliever or prevents daily activity	ER visit or hospitalization
Fatigue/Malaise (unusual tiredness)	No interference with activity	Some interference with activity	Significant; prevents daily activity	ER visit or hospitalization
Generalized myalgia (muscle ache or pain)	No interference with activity	Some interference with activity	Significant; prevents daily activity	ER visit or hospitalization
Generalized arthralgia (joint ache or pain)	No interference with activity	Some interference with activity not requiring medical intervention	Prevents daily activity and requires medical intervention	ER visit or hospitalization

Abbreviations: ER = emergency room; IV = intravenous.

^{*} Oral temperature; no recent hot or cold beverages or smoking.

Sources: Guidance for industry – Toxicity grading scale for heathy adult and adolescent volunteers enrolled in preventative vaccine clinical trials; Tables for clinical abnormalities (DHHS 2007). Division of AIDS Grading the Severity of Adult and Pediatric Adverse Events (DHHS 2014).

Table 7: Tables for Laboratory Abnormalities

Serum Chemistry*	Mild (Grade 1)	Moderate (Grade 2)	Severe (Grade 3)	Potentially Life-threatening (Grade 4)**

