4.1 Primary Endpoints

The primary endpoints for the study are the following:

- Frequency and grade of each solicited local and systemic reactogenicity adverse reaction (AR) during a 7-day follow-up period after each vaccination
- Frequency and grade of any unsolicited adverse events (AEs) during the 28-day follow-up period after each vaccination
- Frequency of any medically attended adverse event (MAAE), serious adverse event (SAE), and adverse event of special interest (AESI) from Day 1 to the end of study (EOS) Visit at Month 13

Other safety assessments include clinical laboratory test results (hematology, serum chemistry, and coagulation); vital sign measurements; and physical examination findings.

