7.6.2.1 Overview of Adverse Events

An overall summary of unsolicited TEAEs including the number and percentage of participants who experience the following will be presented:

- All unsolicited TEAEs
- All unsolicited serious TEAEs
- All unsolicited TEAEs leading to death

- All unsolicited TEAEs leading to vaccination discontinuation
- All unsolicited TEAEs of grade 3 or 4
- All unsolicited TEAEs of special interest
- All unsolicited medically-attended TEAEs

The table will also include number and percentage of participants with unsolicited, treatment-related TEAEs in each of the above categories.

The overall summary will also be summarized separately for flavivirus seropositive and seronegative participants.

In addition, listings containing individual participant data for TEAEs, TEAEs leading to vaccination discontinuation, SAEs, AESIs, and medically-attended TEAEs will be provided separately.

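### The solicited-reaction table for the first primary endpoint names Grades 1, 2, 3 and any grade, but no Grade 4 or Grade 3-or-higher row

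*SAP*

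**What the plan says.** Protocol 3.6.1 sets the first primary endpoint as "Frequency and grade of each solicited local and systemic reactogenicity AE during a 7-day follow-up period after each vaccination", and SAP 4.1 repeats it: "Frequency and grade of each solicited local and systemic reactogenicity adverse reaction (AR) during a 7-day follow-up period after each vaccination". Protocol 3.6.6.2 adds that reactogenicity is to be summarised by severity.

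SAP 7.6.1 specifies one summary of solicited reactions by grade. They "will be tabulated by grade (including grades 1, 2, 3, and any grade >0"), by treatment group and vaccination, with the same summary repeated for seropositive and seronegative participants. The same section's Table 2 has a Grade 4 column. Its fever row reads "Fever | 38.0 – 38.4°C | 38.5 – 38.9°C | 39.0 – 40.0°C | > 40.0°C", and its Grade 4 cells for erythema and swelling are blank.

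For unsolicited events, SAP 7.6.2.1 does name the top of the scale: "All unsolicited TEAEs of grade 3 or 4". SAP 7.6.2.3 also has Grade-3-or-higher tables, again for unsolicited events only.

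**The concern.** An endpoint defined by grade should be reported over every grade the plan can assign. Grade 4 is a working category here. It is derived for fever in the SAP, defined for most solicited reactions in protocol Appendix 3, and used in pause rule 2, where one participant is enough: "Any Grade 4 adverse event that cannot be reasonably attributed to a cause other than vaccination".

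If the table stops at Grade 3, a dose level with a Grade 4 reaction shows the same Grade 3 percentage as a dose level without one. The interim summaries by dose group are meant to inform dose selection (protocol 3.6.8). It is the rate by dose at the severe end that would be incomplete.

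**Working it through.** **1. Which solicited reactions can be Grade 4.** Protocol 3.5.6 lists 3 local and 8 systemic solicited items, 11 in all. Protocol Table 6 gives a Grade 4 criterion for all 3 local items (for erythema, "Necrosis or exfoliative dermatitis"). It gives one for 6 of the 8 systemic items: fever, nausea/vomiting ("ER visit or hospitalization for hypotensive shock"), headache, fatigue, myalgia and arthralgia. That is 3 + 6 = 9 of 11. Chills and rash have no row in Table 6 as printed.

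**2. Whether another summary picks up Grade 4.** Take a diary fever above 40.0 °C on one day that resolves, with no withdrawal and no medical visit.
- *Entry as an AE (SAP 7.6.1).* The criteria are study withdrawal, vaccine withdrawal, duration beyond 7 days, seriousness, or a Grade 3 or greater laboratory or vital-sign result. Only the last could apply.
- *Vital-sign route.* Protocol 3.5.9 counts body temperature as a vital sign, but the vital-sign part of Table 6 says fever is graded under systemic reactions. Scheduled vital signs are taken only at screening, Day 1 and Day 29 (protocol Table 5). This route is doubtful for a diary fever.
- *Unsolicited tables (SAP 7.6.2.1 to 7.6.2.3).* A solicited reaction is stated to be recorded as unsolicited as well only if it is serious (SAP 7.6.2).

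No planned summary of solicited reactions therefore names a Grade 4 or Grade-3-or-higher rate. SAP Section 8 does not list this as a change from the protocol.

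**3. Size.** The inputs from SAP Table 1 are 24 vaccinees per dose level, of whom 4 are seropositive and 20 seronegative.
- One Grade 4 participant: 1/24 = 4.2% of the dose group, 1/4 = 25% of seropositive vaccinees, 1/20 = 5% of seronegative vaccinees. Counted at maximum grade, the participant is in none of the three numbered rows.
- Hypothetical example: 1 Grade 3 and 2 Grade 4 fevers among 24. The highest numbered row shows 1/24 = 4.2%, and Grade 3 or higher is 3/24 = 12.5%.

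**4. How plausible a Grade 4 case is.** The SAP 5.2 figures reproduce from 1 − (1 − p)^24. At p = 0.10 the result is 1 − 0.90^24 = 0.920 (stated 92%), and at p = 0.05 it is 1 − 0.95^24 = 0.708 (stated 70.8%). The documents give no Grade 4 incidence, so the values below are assumptions. All mRNA-1893 recipients number 4 × 24 = 96.

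| Assumed Grade 4 incidence | At least 1 in 24 | At least 1 in 96 |
|---|---|---|
| 0.5% | 11% | 38% |
| 1% | 21% | 62% |
| 2% | 38% | 86% |

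**5. Whether Grade 4 can be recovered by subtraction.** If each participant is counted once at maximum grade, Grade 4 = any − (Grade 1 + Grade 2 + Grade 3). SAP 7.6.2.2 and 7.6.2.3 state a maximum-severity rule for unsolicited events, but 7.6.1 states none for solicited reactions. Without it the subtraction can fail. Suppose one participant has Grade 4 only, and a second has Grade 1 on one day and Grade 2 on another and is counted in both rows. Then any = 2, Grades 1 to 3 sum to 1 + 1 + 0 = 2, and the difference is 0 although one Grade 4 occurred.

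**The case against.** A reader might infer that the plan excludes Grade 4 from the table, or that a Grade 4 reaction would go unnoticed. The documents do not support either reading.

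- *The list may not be exhaustive.* SAP 7.6.1 introduces the grades with the word *including*, and the table shells that SAP 7.1 mentions are not in the documents. The row list is the natural reading, not an explicit exclusion.
- *The event remains visible.* All solicited reactions are listed by participant (SAP 7.6.1), and the pre-identified sponsor staff unblinded at the Day 57 interim review individual listings (protocol 3.4.5). A Grade 4 event not reasonably attributed to another cause suspends dosing and enrollment in the cohort and convenes the SMC. With 24 vaccinees per dose, a listing shows a rare event well.
- *Many Grade 4 cases have another route.* Most Table 6 criteria are an emergency-room visit or hospitalization. Protocol 3.5.6 collects AEs needing an unscheduled visit or medical attention, medically attended AEs are a primary endpoint with their own overview row, and serious solicited reactions are also recorded as unsolicited AEs. It would be too much to say that no Grade 4 solicited reaction can reach a summary table.
- *The 12.5% example is hypothetical.* A second vaccine-attributable Grade 4 fever in one cohort would have to occur despite the pause triggered by the first.
- *A bare Grade 4 row could mislead.* Because Table 2 leaves Grade 4 blank for erythema and swelling, the row would show 0% for them by construction.

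All five points stand and limit the severity. None of them supplies a Grade 4 or Grade-3-or-higher rate by dose for solicited reactions.

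**Conclusion.** The gap is real and minor. Taken as the row list, SAP 7.6.1 gives the first primary endpoint no Grade 4 or Grade-3-or-higher rate by dose, while the same section derives Grade 4 fever. A non-serious Grade 4 reaction without medical attention, such as a brief diary fever above 40.0 °C, would count only under any grade in that table. Each such participant is 4.2% of a dose group of 24.

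This rests on two assumptions: that the named grades are the rows, and that a diary fever does not enter the AE tables through the vital-sign criterion. It is incomplete reporting of a primary endpoint, not a missed safety signal, because the listings and pause rule 2 still show the event. No sample size, analysis set, denominator or error rate is affected.

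**What to change.** In SAP 7.6.1, for the overall and by-serostatus tables, list Grades 1, 2, 3, 4, Grade 3 or higher, and any grade. State that each participant is counted once, at maximum grade, per reaction and vaccination.

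For erythema and swelling, reconcile the blank Grade 4 cells of SAP Table 2 with protocol Table 6, or mark Grade 4 as not derived, so that it is not shown as an automatic 0%. If no Grade 4 criterion exists for chills or rash, mark those cells the same way.

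The cost is a short change of wording, a table note and two more rows. No new data are needed, so this is a free improvement apart from those rows. If the shells already carry a Grade 4 row, only the SAP wording needs aligning, with Grade 3 or higher and the counting rule added if they are absent.
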